Appendix 4 Directionality of Worst Laboratory Parameters

Laboratory Test	Parameter	Worst Value
Hematology	Hematocrit	Lowest value
	Hemoglobin	Lowest value
	Red blood cell count	Lowest value
	Mean cell hemoglobin	Lowest value
	Mean cell hemoglobin concentration	Lowest value
	Mean cell volume	Lowest value
	White blood cell count	Lowest value
	Platelets	Lowest value
	Neutrophils	Lowest value
	Lymphocytes	Lowest value
	Monocytes	Lowest value
	Eosinophils	Highest value
	Basophils	Lowest value
	Chemistry	Albumin
Alkaline phosphatase		Highest value
Alanine aminotransferase ALT/SGPT)		Highest value
Amylase		Highest value
Aspartate aminotransferase (AST/SGOT)		Highest value
Urea		Highest value
Bicarbonate		Lowest value
Calcium		Both highest value and lowest value
Cholesterol		Highest value
Chloride		Both highest value and lowest value
Creatinine		Highest value
Creatine kinase (CK)		Highest value
Gamma-glutamyl transpeptidase (GGT)		Highest value
Blood glucose		Both highest value and lowest value
Lactate dehydrogenase (LDH)		Highest value
Lipase		Highest value
Magnesium		Both highest value and lowest value
Phosphate		Both highest value and lowest value
Potassium		Both highest value and lowest value
Sodium		Both highest value and lowest value
Total bilirubin		Highest value
Total protein		Lowest value
Uric acid		Highest value
Coagulation	International normalized ratio (INR)	Highest value

Appendix 5 Modified Division of Microbiology and Infectious Diseases Adult Toxicity Table

The DMID Adult Toxicity Table (21-Nov-2007) was modified to exclude the clinical component of the toxicity grading because clinical signs and symptoms related to abnormal laboratory values are not collected in this study. In addition, Grade 0 was added to the table so that shifts from normal could be analyzed. The grades for several parameters including enzymes were modified to ensure that any possible numeric value can be categorized appropriately (eg, for creatinine, Grade 3 is defined as “>1.5-3.0×ULN” instead of “1.6-3.0×ULN”).

For toxicity grades based on a multiple of the ULN, the normal range from the central laboratory will be applied.

For toxicity grades based on fixed values, the grades will be assigned regardless of the normal actual range values from the central laboratory. For example, a hemoglobin value of 10.0 gm/dL will be assigned a grade of 1 toxicity, even if the lower limit of normal from the laboratory was 9.8 gm/dL.

HEMATOLOGY

	Grade 0	Grade 1	Grade 2	Grade 3	Grade 4
Hemoglobin (gm/dL)	> 10.5	9.5-10.5	8.0-9.4	6.5-7.9	< 6.5
Absolute Neutrophil Count (count/mm ³)	> 1500	1000-1500	750-999	500-749	< 500
Platelets (count/mm ³)	≥ 100,000	75,000-99,999	50,000-74,999	20,000-49,999	< 20,000
WBCs (count/mm ³)	1000-10,999	11,000-12,999	13,000-14,999	15,000-30,000	> 30,000 or < 1,000

COAGULATION

	Grade 0	Grade 1	Grade 2	Grade 3	Grade 4
Prothrombin time (PT) (sec)	≤1 x ULN	1.01-1.25 x ULN	1.26-1.5 x ULN	1.51 x 3.0 x ULN	> 3 x ULN
Activated partial thromboplastin time (aPTT) (sec)	Increased	≤ ULN	1.01 - 1.66 x ULN	1.67 - 2.33 x ULN	2.34 - 3 x ULN
International normalized ratio (INR)	Increased	≤ ULN	> 1 - 1.5 x ULN	> 1.5 - 2.5 x ULN	> 2.5 x ULN

CHEMISTRY

	Grade 0	Grade 1	Grade 2	Grade 3	Grade 4
Hyponatremia (mEq/L)	> 135	130-135	123-129	116-122	< 116
Hypernatremia (mEq/L)	< 146	146-150	151-157	158-165	> 165
Hypokalemia (mEq/L)	> 3.4	3.0-3.4	2.5-2.9	2.0-2.4	< 2.0
Hyperkalemia (mEq/L)	< 5.6	5.6-6.0	6.1-6.5	6.6-7.0	> 7.0
Hypoglycemia (mg/dL)	≥ 65	55-64	40-54	30-39	< 30
Hyperglycemia (mg/dL) (nonfasting and regardless of prior history of diabetes)*	< 116	116-160	161-250	251-500	> 500
Hypocalcemia (mg/dL) (corrected for albumin)*	> 8.4	8.4-7.8	7.7-7.0	6.9-6.1	< 6.1
Hypercalcemia (mg/dL) (correct for albumin)*	≤ 10.5	10.6-11.5	11.6-12.5	12.6-13.5	> 13.5
Hypomagnesemia (mEq/L)	> 1.4	1.4- 1.2	1.1-0.9	0.8-0.6	< 0.6
Hypophosphatemia (mg/dL)	≥ 2.5	2.0-2.4	1.5-1.9	1.0-1.4	< 1.0
Hyperbilirubinemia (total bilirubin)	< 1.1×ULN	1.1-1.5×ULN	> 1.5- 2.5×ULN	> 2.5-5×ULN	> 5×ULN
Urea	< 1.25×ULN	1.25-2.5×ULN	> 2.5-5×ULN	> 5-10×ULN	>10×ULN
Hyperuricemia (uric acid) (mg/dL)	< 7.5	7.5–10.0	10.1–12.0	12.1–15.0	> 15.0
Creatinine	< 1.1×ULN	1.1-1.5×ULN	> 1.5- 3.0×ULN	> 3.0-6×ULN	> 6×ULN

*The DMID toxicity table reports hyperglycemia detected in nonfasting specimens obtained from subjects with no prior diabetes.

ENZYMES

	Grade 0	Grade 1	Grade 2	Grade 3	Grade 4
AST (SGOT)	< 1.25×ULN	1.25-2.5×ULN	> 2.5-5×ULN	> 5-10×ULN	> 10×ULN
ALT (SGPT)	< 1.25×ULN	1.25-2.5×ULN	> 2.5-5×ULN	> 5-10×ULN	> 10×ULN
GGT	< 1.25×ULN	1.25-2.5×ULN	> 2.5-5×ULN	> 5-10×ULN	> 10×ULN
Alkaline Phosphatase	< 1.25×ULN	1.25-2.5×ULN	> 2.5-5×ULN	> 5-10×ULN	> 10×ULN
Amylase	< 1.1×ULN	1.1-1.5×ULN	> 1.5-2.0×ULN	> 2.0-5.0×ULN	> 5.0×ULN
Lipase	< 1.1×ULN	1.1-1.5×ULN	> 1.5-2.0×ULN	> 2.0-5.0×ULN	> 5.0×ULN

* Calcium corrected for albumin = [0.8 x (normal albumin - subject's albumin)] + serum Ca level
 Where normal albumin = 4 g/dl, albumin is in g/dL and calcium is in mg/dL

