33 PRESTUDY DOCUMENTATION

The investigator must provide the sponsor with the following documents BEFORE enrolling any subjects:

- Completed and signed form 1572
- All applicable country-specific regulatory forms
- Current signed and dated curricula vitae for the investigator, sub-investigators, and other individuals having significant investigator responsibility who are listed on the form 1572 or equivalent, or the clinical study information form
- Copy of the IRB/IEC/REB approval letter for the protocol and informed consent. All advertising, recruitment, and other written information provided to the subject must be approved by the IRB/IEC/REB. Written assurance of continuing approval (at least annually) as well as a copy of the annual progress report submitted to the IRB/IEC/REB must also be provided to the sponsor.
- Copy of the IRB/IEC/REB-approved informed consent document to be used
- Where applicable, a list of the IRB/IEC/REB members and their qualifications, and a description of the committee's working procedure
- Copy of the protocol sign-off page signed by the investigator
- Fully executed CSA
- Where applicable, a financial disclosure form
- A written document containing the name, location, certification number, and date of certification of the laboratories to be used for laboratory assays and those of other facilities conducting tests. This document should be returned along with the statement of investigator form. The sponsor must be notified if the laboratory is changed or if any additional laboratory is to be used.
- List of normal laboratory values and units of measure for all laboratory tests required by the protocol. This is required for each laboratory to be used during the study. The sponsor must be notified if normal values or units of measurement change.

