11.4 Laboratory Values

Summaries of laboratory data will include hematology, chemistry and coagulation (INR only) parameters. Laboratory parameters will be presented in alphabetic order with the following exceptions: differentials of white blood cell (WBC) counts will be presented following the WBC results, and chemistry parameters will first be grouped by organ class (renal, liver, electrolytes, and other) and presented alphabetically within each of these classes, as shown in [Table 9](#).

Table 9. Laboratory Parameters and Organ Class

Organ Class	Laboratory Parameter
Renal	Creatinine
Renal	Urea
Liver	Alkaline phosphatase (ALP)
Liver	ALT
Liver	AST
Liver	Total Bilirubin
Liver	GGT
Electrolytes	Bicarbonate
Electrolytes	Calcium
Electrolytes	Chloride
Electrolytes	Magnesium
Electrolytes	Potassium
Electrolytes	Sodium
Other	Albumin
Other	Amylase
Other	Blood glucose
Other	Cholesterol
Other	CK
Other	CK isoenzyme
Other	LDH
Other	Lipase
Other	Phosphate
Other	Total protein
Other	Uric acid

Baseline is defined as the central lab value closest to and prior to the first dose of test article. If no central lab value is available prior to the first dose of test article the local lab value that is closest to and prior to the first dose of test article will be used as baseline. For by visit analyses, central lab values will be used unless no central lab value was obtained in the visit window. In this case, local lab values will be used for the by visit analyses. All lab values (central and local) are used for determination of the overall worst post-baseline value.

Several analyses of the laboratory data will be presented. Descriptive statistics (based on SI units) for chemistry and hematology values and the change from baseline will be summarized by treatment group at each time point (Day 3 [+ 1 day], Day 7 [+1 day], Day 10 [+1 day], EOT visit and PTE visit), and for the overall worst value post-baseline (which includes unscheduled visits). [Appendix 4](#) provides the directionality of the worst values for each laboratory parameter.

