Clinically notable laboratory values will be determined based on the modified Division of Microbiology and Infectious Diseases (DMID) criteria in [Appendix 5](#). Shift tables will be presented to show the number of subjects with a laboratory value with a grade of 0, 1, 2, 3 or 4 at baseline versus the value at each visit and the worst post-baseline value. Number and percentage of subjects with at least a 2 grade increase from baseline (based on DMID criteria) will be summarized by treatment arm. Percentages for each laboratory test will be based on the number of subjects with a baseline and post-baseline evaluation of the specific laboratory test. A listing

will be provided which gives all laboratory results for a given laboratory test for subjects who have at least a 2 grade increase from baseline.

The number and percentage (based on the number of subjects with a normal level at baseline) of subjects in each treatment group with an elevated transaminase level ($> 3 \times \text{ULN}$, $> 5 \times \text{ULN}$, and $>10 \times \text{ULN}$), an elevated bilirubin level ($>1.5 \times \text{ULN}$ and $>2 \times \text{ULN}$) will be presented by study visit. A table will list all subjects with any post-baseline ALT or AST $> 3x \text{ULN}$ or total bilirubin $>1.5 \times \text{ULN}$. The table will provide the AST, ALT, total bilirubin and alkaline phosphatase value for each subject at each time point laboratory values were entered. A listing of subjects who meet the laboratory criteria for Hy's law will also be provided. The laboratory criteria for Hy's law is defined as 1) ALT or AST $> 3 \times \text{ULN}$, ALP $\leq 2.0 \times \text{ULN}$, and total bilirubin $> 1.5 \times \text{ULN}$ and 2) ALT or AST $> 3 \times \text{ULN}$, ALP $\leq 2.0 \times \text{ULN}$, and total bilirubin $> 2 \times \text{ULN}$.

Detailed subject listings of all laboratory data (local and central laboratory data) collected during the study will be provided, including calculated creatinine clearance (using the Cockcroft-Gault equation). Laboratory values outside normal limits will be identified in the subject data listings with flags for low (L) and high (H) as will laboratory values that meet the clinically notable thresholds (CN).

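### Local laboratory results are graded against the central laboratory's upper limit of normal, which can create or hide grade shifts in the descriptive safety tables

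*SAP*

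**What the plan says.** SAP section 11.4 sets the grading scheme: "Clinically notable laboratory values will be determined based on the modified Division of Microbiology and Infectious Diseases (DMID) criteria in" Appendix 5. The shift tables compare the baseline grade "versus the value at each visit and the worst post-baseline value". A further summary gives the "Number and percentage of subjects with at least a 2 grade increase from baseline".

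The same section lets local results into each of these inputs:

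- **Baseline.** If there is no pre-dose central value, "the local lab value that is closest to and prior to the first dose of test article will be used as baseline".
- **Visits.** Central values are used unless none falls in the window. "In this case, local lab values will be used for the by visit analyses".
- **Worst value.** "All lab values (central and local) are used for determination of the overall worst post-baseline value". This is not a fallback; it applies to every subject with a local result.

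Appendix 5 then fixes the reference limit: "For toxicity grades based on a multiple of the ULN, the normal range from the central laboratory will be applied". Appendix 4 defines the worst value of each affected parameter that it lists as the highest raw result.

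Protocol section 33 asks sites for lists of normal values and units for protocol-required tests, and says "This is required for each laboratory to be used during the study". The SAP makes no use of those lists in grading.

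**The concern.** A multiple of the upper limit of normal (ULN) expresses a result relative to the range of the laboratory that produced it. Dividing one laboratory's result by another's limit does not give that multiple unless the two limits agree. Nothing in the SAP rescales local results, leaves them out of grading, or grades them by their own range.

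The parameters affected are those that Appendix 5 grades by ULN multiple: ALT, AST, GGT, alkaline phosphatase, total bilirubin, creatinine, urea, amylase, lipase, and prothrombin time and INR. Appendix 5 also has an aPTT row, but section 11.4 limits the coagulation summaries to INR. Grades on fixed values, such as hemoglobin, platelets, sodium and potassium, use no reference range and are not affected.

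At stake are the grade shift tables and the count of subjects with an increase of two or more grades. A central baseline paired with a local worst value is the obvious case: a difference between reference limits then appears as, or conceals, a change in the subject.

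**Working it through.** The plan states no figure to reproduce. The check traces which values are graded and against which limit, then applies the Appendix 5 cut-points to examples.

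**Inputs from Appendix 5 (multiples of ULN).** The tabulated bands are used throughout; the appendix's introductory example labels the creatinine band above 1.5 to 3.0 as Grade 3, while the table has it as Grade 2.

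| | Grade 0 | Grade 1 | Grade 2 | Grade 3 |
|---|---|---|---|---|
| ALT | < 1.25 | 1.25–2.5 | > 2.5–5 | > 5–10 |
| Creatinine | < 1.1 | 1.1–1.5 | > 1.5–3.0 | > 3.0–6 |
| Lipase | < 1.1 | 1.1–1.5 | > 1.5–2.0 | > 2.0–5.0 |

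**Assumed inputs.** The documents give no ULNs. Let r = central ULN / local ULN, taken between 0.7 and 1.5. A result that is m times its own local ULN is graded, as written, at m / r.

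**ALT, local ULN 60 and central ULN 40 (r = 0.67, just outside that range).**
- Result 110: 110/60 = 1.83, Grade 1. As written, 110/40 = 2.75, Grade 2. From a Grade 0 baseline, a one-grade rise becomes a counted two-grade increase.
- Result 70: 70/60 = 1.17, Grade 0. As written, 70/40 = 1.75, Grade 1.
- With the two limits exchanged the error reverses: 110/40 = 2.75 (Grade 2) would be graded 110/60 = 1.83 (Grade 1).

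**Other values of r.**

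| Result (× local ULN) | r | m / r | Own-range grade | Grade as written |
|---|---|---|---|---|
| ALT 2.3 | 0.9 | 2.56 | 1 | 2 |
| ALT 2.8 | 1.25 | 2.24 | 2 | 1 |
| Creatinine 1.6 | 1.1 | 1.45 | 2 | 1 |
| Creatinine 1.6 | 1.5 | 1.07 | 2 | 0 |
| Creatinine 1.08 | 0.7 | 1.54 | 0 | 2 |
| Lipase 2.1 | 1.25 | 1.68 | 3 | 2 |
| Lipase 2.1 | 1.5 | 1.40 | 3 | 1 |

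At r = 1 no grade changes.

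**Why ALT differs from creatinine and lipase.** Each ALT cut-point is twice the one before (1.25, 2.5, 5, 10), so limits that differ by no more than a factor of 2 move an ALT result by at most one grade. The creatinine Grade 1 band spans only 1.5/1.1 = 1.36, and the lipase Grade 2 band only 2.0/1.5 = 1.33. A larger difference in limits can carry a result across a whole band, which is two grades.

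**Selection of the worst value.** Keep the ALT limits of 60 and 40, and suppose one subject has a local 110 and a central 105. The highest raw result is 110. If only the grading sentence were changed, the subject would be shown at 110/60 = 1.83, Grade 1. The central result, 105/40 = 2.63, Grade 2, would drop out of the worst-value table. Grading and selection must therefore be changed together.

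**The case against.** The strongest defence is that one common ULN is a deliberate and consistent yardstick. It keeps the raw ranking in Appendix 4 aligned with the grade. If laboratories run comparable assays but set different limits, own-range grading would give identical results different grades. This does not rescue the rule. Nothing in the documents shows that local and central assays are harmonised, and protocol section 33 asks for each laboratory's own normal values. The point about ranking does stand: as the last step of the working shows, changing the grading sentence alone is not enough.

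A second defence is that the reach is small, and this stands. Protocol section 16.1.2 sends every scheduled post-Screening sample, and a second Screening sample, to the central laboratory. Local baseline and visit values are fallbacks. Local results enter routinely only through the worst-value rule, from the optional extra tests in protocol section 16.1.3.4. SAP section 11.4 also lists all local and central results, so a spurious shift can be seen on review; a hidden one is harder to find.

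A reader might infer three stronger things that the documents do not support:

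- *Wrong grades concentrate where a problem was suspected.* This is plausible, but the protocol describes extra local tests only as part of routine standard of care.
- *The comparison between arms is biased.* Treatment is double-blind, and nothing links local testing to arm.
- *The local ranges are already in the database.* Section 33 requires lists to be filed for protocol-required tests. It does not say that they are entered as data, and additional tests may not be covered.

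Restricting ULN-based grading to central values would be another coherent rule, and it fits the statement in protocol section 16.1.2 that the central laboratory serves the safety analysis. Its price is that local results, including some that may be the worst observed, would go ungraded.

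**Conclusion.** The concern holds as a minor defect in the descriptive safety analysis. Followed literally, the SAP grades local results against a limit that belongs to another laboratory, and this can create or hide a grade shift or a two-grade increase. If the Appendix 5 sentence was meant for central results only, local results have no grading rule, and the text still needs correcting.

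In the examples, a 10% to 25% difference in limits moves some results by one grade. A difference of 30% to 50% moves some creatinine and lipase results by two. ALT moves by at most one grade for limits within a factor of 2. These sizes rest on assumed ULNs. How many results would be affected, and in which direction on balance, cannot be determined from the documents. It would go too far to conclude that the laboratory safety tables as a whole are unreliable: fixed-value grades and centrally tested results are not affected, and neither is the primary efficacy analysis.

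A related gap is that section 11.4 names no ULN source for the transaminase, bilirubin and Hy's law thresholds. With the assumed ALT limits, 3 × 40 = 120 and 3 × 60 = 180, so a local ALT above 120 and up to 180 exceeds three times the ULN by the central range but not by its own.

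**What to change.** Make three linked changes before database lock:

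1. **Appendix 5.** State that grades defined as a multiple of the ULN use the reference range of the laboratory that performed the test. Use the central range only when no local range is on file, and flag those results.
2. **Section 11.4 and Appendix 4.** For these parameters, define the worst post-baseline value as the highest grade, or the highest multiple of the applicable ULN, in place of the highest raw result.
3. **Section 11.4.** Apply the same ULN rule to the transaminase, bilirubin and Hy's law thresholds, including what counts as a normal level at baseline.

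The cost is a few lines of SAP text and some programming. The local range lists required by protocol section 33 may have to be entered and merged with the results. Ranges for additional local tests outside the protocol may be missing, which is why the flagged fallback is needed. No new subject data are required.
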